### **Aim 3: Assess preliminary outcomes of the peer mentoring program.**

*Hypothesis 3 (Phase 2):* Participants in the mentor group will demonstrate improvement in self-management skills, transition readiness, and anxiety.

*Hypothesis 4 (Phase 3):* Participants in the self-management + peer mentor intervention will demonstrate greater improvement in transition readiness than participants in the usual care group.

*Hypothesis 5 (Phase 3):* Participants in the self-management + peer mentor intervention will participate in survivorship and preventive healthcare at greater rate than participants in the usual care group.

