### **3. Research Design and Methods**

This research will be conducted in three phases. In Phase 1, we will use provider, survivor, and caregiver interviews to adapt PSST to focus on AYA self-management of care and develop the intervention. In Phase 2, we will conduct a single arm pilot test of the program with 40 young adult survivors ages 18-25 years and 20 peer mentors. Based on feedback collected in Phase 2, we will refine the online modules and conduct usability testing of the new modules in Phase 3A. We will then evaluate the feasibility and preliminary efficacy of the self-management + peer mentoring intervention in a randomized two-arm trial comparing the intervention to usual care (Phase 3B). The biostatistician will determine a randomization scheme using an undisclosed block size. The scheme will be uploaded to DatStat for automatic assignments. For a backup, randomization assignments will be provided to PI in sealed envelopes as well.

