### **3.3 Sample Size Justification**

Phase 1: Total sample size is 24-28, including 10 AYA survivors, 10 parents of AYA survivors, and 4-8 physicians who work with AYA survivors. Qualitative data will be analyzed on a continuing basis. Pooling data across participants, we expect 24-28 interviews will be adequate to achieve data saturation (that is, no new themes emerge from additional participants).

Phase 2: 40 AYA survivors and 20 peer mentors will be recruited for the pilot trial to evaluate feasibility (primary objective) and preliminary outcomes (secondary objective). As this is a feasibility study, we recognize we are underpowered to detect small or medium effects. Published data suggest 5-9% of survivors are African American or Hispanic; data from the NJSCR show greater diversity, with 11.6% of patients diagnosed with cancer at age 10-19 during the period of 2008-2012 reporting as African American, 19% reporting as Hispanic, and 5.7% as Asian American/Pacific Islander. We will oversample these groups.

Phase 3A: Up to 20 AYA survivors will be recruited for usability testing of the online intervention. Given the preliminary work conducted in Phase 2, we expect 12-20 sessions will achieve data saturation (i.e., no new issues emerge according to pre-specified stopping criteria). Usability testing is designed to be iterative in that changes can be made to the site after a small number of participants. Therefore, participants who agree may be asked to complete multiple usability sessions over the course of a few months to provide additional feedback on changes or new features added. Thus we expect about 12 to 20 participants will be needed to achieve data saturation.

Phase 3B: Total sample size is 50 AYA survivors. We chose the sample size and decision rules so that the probability of declaring feasibility would be approximately 5% under unacceptable rates of acceptance/completion and exceed 95% under acceptable rates. If true acceptance and completion rates were 41% and 70%, respectively, which we consider too low to move to an efficacy trial, then the probability of declaring feasibility would be 5%.

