## Promoting Follow-Up Care Self-Management for Adolescent and Young Adult (AYA) Childhood Cancer Survivors

[name], MPH

ion			the follow-up		
-----	--	--	---------------	--	--

Sample size was based on the primary feasibility aim, but we also calculated detectable group difference in the primary outcome of the RTQ Adolescent Responsibility total score at the 6-week post-intervention time. Based on survey data, we expect AYA survivors to score an average of 2.57 ( $SD = 0.83$ ) at baseline. Using an independent t-test assuming the control group remains at baseline levels and two-sided alpha of .05, we have 80% power to detect a group difference of 0.66 in the outcome. This would represent the intervention group increasing from “sometimes” to “often” being responsible, which we consider clinically meaningful.

Up to 20 mentors will participate. Mentors will be matched 1:1 with AYA survivors; each mentor may agree to work with up to 5 individuals. As in Phase 2, we expect that several mentors will choose to mentor more than one individual, so a sample size of up to 20 is reasonable.

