### Phase 3B:

**Data Management:** The same procedures used in Phase 2 will be used in Phase 3B, with the exception that TigerConnect (previously called TigerText) will be used for secure messaging as well as secure videoconferencing (instead of doxy.me). Additionally, TigerConnect now allows for secure file transfer so that peer mentors can securely transfer audio recordings to the study team either via Rutgers LiFT or TigerConnect. For participants who consent to be contacted for future studies, the study team will store their contact information separately from research records on the PI's secure One Drive, with access granted only to the PI, study coordinator, and limited authorized research staff. We will store this information for up to 10 years from date of consent.

We will utilize HIPAA compliant Qualtrics survey tool to request the name and contact information of the physician they have seen in the past 12 months to understand their health care utilization during the study period and to obtain their electronic signature on the Release of Medical Record form. Any paper copies will be kept in a locked filing cabinet in the PI's office.

**Data Analysis:** We will examine feasibility through study enrollment rates, retention rates, usability/engagement with online modules and peer mentor, barriers to engagement, and reasons for study drop out. Descriptive analyses (frequencies, means, confidence intervals) will be used to evaluate hypotheses regarding enrollment ( $>50\%$ ), retention ( $>80\%$  complete all surveys), and intervention completion ( $>75\%$  modules/mentor calls). Multilevel modeling (MLM) will be used to examine differences between the intervention and usual care groups over time on transition readiness (RTQ Adolescent Responsibility and TRI total scores). Our primary analysis will consider both time and treatment to be categorical with an interaction between the two. The interaction will be assessed to determine whether change in transition readiness differs between the two groups. The MLM approach assumes any missing observations are missing at random but includes all observed data. Exploratory analyses of additional outcomes (e.g., self-efficacy, adherence to medical appointments and screenings, and health behaviors) will use the identity link or the logit link as appropriate for continuous or binary outcomes.

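### Section 3.3 makes RTQ Adolescent Responsibility the primary efficacy outcome, but the Phase 3B primary analysis in Section 5 sets TRI beside it unranked, so the plan does not settle which scale carries Hypothesis 4

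*Combined protocol and SAP*

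**What the plan says.** Four places bear on this.

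- **Section 1.1, Aim 3, Hypothesis 4.** Intervention participants "will demonstrate greater improvement in transition readiness than participants in the usual care group". No instrument is named.
- **Section 3.3, Phase 3B.** The sample size rests on feasibility, but a detectable difference is also given for the "primary outcome of the RTQ Adolescent Responsibility total score". With "two-sided alpha of .05, we have 80% power to detect a group difference of 0.66 in the outcome", this is the only efficacy power statement for Phase 3B. TRI is not mentioned there.
- **Section 4.2.** RTQ and TRI are described as different instruments: RTQ concerns responsibility for care tasks, while TRI also covers knowledge, attitudes and beliefs. In the Phase 3B schedule RTQ is collected at four time points and TRI at three.
- **Section 5, Phase 3B, Data Analysis.** The multilevel model examines group differences over time "on transition readiness (RTQ Adolescent Responsibility and TRI total scores". The text continues: "Our primary analysis will consider both time and treatment to be categorical with an interaction between the two". The decision sentence is: "The interaction will be assessed to determine whether change in transition readiness differs between the two groups". Only additional outcomes, such as self-efficacy, adherence and health behaviors, are then called exploratory.

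The documents give no testing order for RTQ and TRI, no multiplicity adjustment, and no rule on whether one or both must succeed.

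**The concern.** Sections 3.3 and 5 do not agree on what carries the Phase 3B efficacy claim. In Section 3.3 it is one scale. In Section 5 two scales share the primary model, and the conclusion is drawn about the construct they have in common. Because TRI is outside the exploratory group, an analyst working from Section 5 could report a difference on TRI alone as confirming Hypothesis 4 without departing from the text.

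The scales measure overlapping but different things, so they may well disagree, and the plan does not say what to conclude if they do. What is at stake is the error rate attached to the Hypothesis 4 claim, and a choice of headline scale that could be made after the data are seen.

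**Working it through.** **Inputs from the documents**

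- Total N = 50 (Section 3.3: "Total sample size is 50 AYA survivors").
- SD 0.83, difference 0.66, two-sided alpha .05, power 80% (Section 3.3).
- Time points: RTQ 4, TRI 3 (Section 4.2 schedule).
- Test: group-by-time interaction with both factors categorical (Section 5).

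**Assumptions, not in the documents**

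- Equal allocation, 25 per arm. Section 3 says only "in a randomized two-arm trial comparing the intervention to usual care".
- RTQ-TRI correlation r, varied from 0 to 0.9.
- .05 applied to each scale. Section 5 does not restate an alpha.
- Within-person correlation over time of 0.5, used only in step 3.

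**Step 1. Reproduce the plan's power figure (RTQ only).**

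Standard error of the difference = 0.83 × √(2/25) = 0.2348.

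Power = Φ(0.66/0.2348 − 1.96) = Φ(2.811 − 1.960) = 80.3%. The noncentral t version gives 78.7%. The stated 80% is reproduced, as one test of one outcome at .05.

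**Step 2. Two tests, either of which may carry the claim.**

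With no effect on either scale and independent tests: 1 − 0.95² = 9.75%.

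With correlated tests: 1 − P(|Z₁| ≤ 1.96 and |Z₂| ≤ 1.96), where Z₁ and Z₂ are bivariate normal with correlation r.

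**Step 3. The same question for the planned interaction tests.**

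Four time points give RTQ a 3-degree-of-freedom interaction test, and three give TRI a 2-degree-of-freedom test. Both were simulated as large-sample Wald tests with 200,000 draws per value of r. The Monte Carlo standard error is about √(0.09 × 0.91/200,000) = 0.06 percentage points.

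| Assumed r | Single-contrast tests (step 2) | Interaction tests (step 3) |
|---|---|---|
| 0 | 9.75% | 9.7% |
| 0.3 | 9.5% | 9.5% |
| 0.5 | 9.1% | 9.2% |
| 0.7 | 8.3% | 8.7% |
| 0.8 | 7.8% | 8.4% |
| 0.9 | 7.0% | 7.7% |

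These figures count a significant difference in either direction. For single-contrast tests, counting only results that favor the intervention, the rate runs from 4.9% (r = 0) to 3.5% (r = 0.9), against a nominal 2.5%.

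**Step 4. The two ways of closing the gap.**

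- RTQ sole primary, TRI secondary: the rate for the Hypothesis 4 claim is 5%, and the calculation in step 1 is unchanged.
- RTQ and TRI co-primary at .025 each: the rate for at least one false positive is 4.9% at r = 0 and 4.0% at r = 0.8. The RTQ critical value rises to 2.241, so power at 0.66 becomes Φ(2.811 − 2.241) = 71.6% (69.0% with the t distribution). The difference detectable with 80% power rises to about 0.74 (t distribution).

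**The case against.** The strongest reply is that Section 3.3 already settles the matter. It names RTQ Adolescent Responsibility as primary, Section 5 lists RTQ first, and TRI is nowhere called primary or co-primary. On this view, the sentence about the primary analysis describes how the model is specified and does not rank outcomes. Adding TRI does not alter the error rate of the RTQ test. This reading is available, and under it the rate is 5%. But Section 5 does not state it: TRI sits inside the primary model and outside the exploratory group, and the decision is worded in terms of the construct.

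Three stronger readings are tempting, and the documents do not support them.

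- **The plan says that either scale is enough.** It does not. It is silent, and silence permits this use without prescribing it.
- **The plan's false-positive rate is 8% to 10%.** Section 5 gives neither an alpha nor a success rule, so the plan has no defined familywise rate. The figure also depends on an assumed correlation. Both scales address transition readiness in the same people, so independence, the top of the range, is the least plausible case.
- **Hypothesis 4 decides whether an efficacy trial follows.** Section 3.3 and its Table 1 tie that step to acceptance and retention. Hypothesis 5 is a second Phase 3 outcome hypothesis, and efficacy is described as preliminary throughout.

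It can also be said that strict error control matters less in a 50-person feasibility pilot. That lowers the weight of the point but does not remove the inconsistency. Section 4.1 says the trial also aims to separate a clinically significant signal from noise, and an unranked second test weakens that distinction.

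**Conclusion.** The point holds as an unresolved inconsistency between Sections 3.3 and 5 about which scale carries Hypothesis 4. Its size is conditional. If either scale may carry the claim at .05, the false-positive rate is roughly 7% to 10%, for assumed correlations from 0.9 down to 0; it remains above 5% throughout that range. If Section 3.3 is held to govern, there is no inflation. The consequence is moderate: the interpretation of a preliminary efficacy result is affected, while the feasibility decision and the sample size are not. The correction is still worth making before the data are analyzed, because it determines what a result on TRI alone may be said to show.

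**What to change.** Add one sentence to the Phase 3B Data Analysis text in Section 5: the RTQ Adolescent Responsibility total score is the sole primary efficacy outcome for Hypothesis 4, as in Section 3.3, and the TRI total score is secondary and supportive. This needs no extra participants and leaves the Section 3.3 power statement as it stands. The cost is that a difference on TRI alone could no longer be reported as confirming Hypothesis 4.

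If the investigators want both scales to be able to carry the claim, the plan should say so and give a multiplicity rule. A split of .025 each would have the power cost shown in step 4, and Section 3.3 would need to be restated.

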#### ***3.1. Duration of Study***

Phase 1: Participants will be asked to complete a one-time interview lasting approximately 60 minutes.

Phase 2: Participants will be asked to complete the intervention over a period of 6 weeks. Participants will be asked to complete 6-week online self-management educational modules and 6 weekly peer mentor calls to facilitate engagement with the online modules and offer specialized support.

Phase 3A: Usability sessions will last approximately 1-hour. Given that usability testing is iterative and design changes are made in response to participant feedback, we will ask some participants if they are willing to review the product another time after changes are made, up to a total of five times. Each session is voluntary and conducted in a way to minimize participant burden.

Phase 3B: Participants assigned to the intervention will be asked to complete it over a period of approximately 8 weeks (which includes 6 peer mentor calls and five corresponding online modules). All participants will be asked to complete surveys at four time points: baseline, immediate post-intervention (~8 weeks after baseline), 3-month follow-up (~5 months after baseline), and 9-month follow-up (~12 months after baseline).

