**Phase 3B:**

Peer mentor eligibility includes:

- (1) age 21-29
- (2) at least 2 years from treatment
- (3) self-reported primary responsibility for care and “complete readiness” to assume responsibility for care or high scores (3 or 4) on all items from the Readiness for Transition Questionnaire

Patient eligibility includes:

- (1) age 18-25
- (2) at least 2 years from treatment for any pediatric cancer diagnosed at age 0-19
- (3) currently does not independently self-manage follow-up care according to self-report (i.e., reports parent is primarily responsible or low readiness to assume total responsibility for care [score of 1 or 2 out of 4 on overall readiness item OR scores <3 on two or more items of the 10-item responsibility scale) using the Readiness for Transition Questionnaire)

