**Promoting Follow-Up Care Self-Management for Adolescent and Young Adult (AYA) Childhood Cancer Survivors**

[name], MPH

Once the Medical Record Release form is completed, signed and returned along with the contact information of the doctors visited in the last 12 months, we will verify the contact information provided by the patient for completeness against publicly available data on the web. We will then mail, email, and/or fax the request for information to the doctor (depending on the contact information available) along with a cover letter and a copy of the signed medical record release form for the patient. We will follow-up with up to three phone calls or emails to the doctor/doctor's office if we do not receive a response to our request. We will request the following information: survivorship care plan/treatment summary (if available), dates and types of visits in the past 12 month (i.e., preventive care, survivorship care, or sick visit) and dates and types of medical screening tests/labs completed in the past 12 months.

Measure	Time Point			
	Baseline	Post-Intervention (~8 weeks)	Follow-Up (~5 months)	Follow-Up2 (~12 months)
Readiness for Transition Questionnaire – Survivor Version (RTQ)	x	x	x	x
Transition Readiness Inventory (TRI)	x	x	x	
Fear of Recurrence Scale 	x	x	x	
Perceived public stigma and internalized shame 	x	x	x	
Self-efficacy (general, cancer-survivorship, health insurance, communication)	x	x	x	x
Follow-Up Care Use and Health Outcomes of Cancer Survivors (FOCUS)	x		x	x
Healthcare Practices (i.e., general physical exam, immunizations, dentist, cancer screenings)	x		x	x
Health behaviors (i.e., tobacco, alcohol, exercise, sedentary)	x	x	x	
PROMIS -Self-Efficacy for Managing Chronic Conditions-Managing Emotions -Information Support -Emotional Support	x	x	x	x (Information & Emotional Support only)
Chronic Disease Self-Efficacy: Communicate with physician scale 	x	x	x	x
Working Alliance Inventory – Short Form 		x		
Internet Intervention Utility Questionnaire, Impact Questionnaire, and Adherence Questionnaire.  &		x		

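### The Phase 3B primary model, as ordinarily read, compares change scores; adjusting for baseline RTQ would generally be more precise at almost no cost

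*Combined protocol and SAP*

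**What the plan says.** Section 5 (Phase 3B, Data Analysis) plans multilevel modelling of two transition-readiness totals, one from the RTQ (Adolescent Responsibility) and one from the TRI, and describes the model this way: "Our primary analysis will consider both time and treatment to be categorical with an interaction between the two". It then gives the test: "The interaction will be assessed to determine whether change in transition readiness differs between the two groups". RTQ is collected at baseline and at about 8 weeks, 5 months and 12 months (Section 3.1 and the schedule in Section 4.2). The text does not say whether baseline means are held equal across arms, gives no baseline covariate and names no covariance structure.

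Section 3.3 says "Sample size was based on the primary feasibility aim" and then adds a detectable difference for the "RTQ Adolescent Responsibility total score at the 6-week post-intervention time", with an expected baseline mean of 2.57 and SD of 0.83: "Using an independent t-test assuming the control group remains at baseline levels and two-sided alpha of .05, we have 80% power" for a difference of 0.66.

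Phase 3B eligibility (Section 3.5.1) selects partly on the same scale. One qualifying route is "scores <3 on two or more items of the 10-item responsibility scale".

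**The concern.** With categorical time that includes baseline, crossed with treatment and left unconstrained, the model has eight free cell means. Each interaction term is then the difference between arms in change from baseline. Under randomisation the arms share a baseline distribution, so any observed baseline difference is chance. A change score subtracts that difference in full, whatever the correlation between visits. Baseline adjustment subtracts only the part that predicts follow-up.

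What is at stake is precision for Hypothesis 4 in a trial of 50. Section 4.1 presents the trial as looking for a clinically significant signal over noise, and the baseline scores are being collected anyway.

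**Working it through.** **Inputs.** From the documents: N = 50, SD 0.83, difference 0.66, two-sided alpha 0.05. Assumed because not stated: 1:1 allocation (25 per arm), follow-up SD 0.83, complete data, and baseline-to-follow-up correlation ρ of 0.3, 0.5 or 0.7. Let k be baseline SD divided by follow-up SD.

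**The plan's own figure.** A two-sample t-test with 25 per arm gives 80.3% (normal approximation) or 78.7% (exact t). The stated 80% reproduces.

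**Variance of the post-intervention contrast**, as a multiple of the single-visit t-test variance (2/25)·0.83² = 0.0551:
- free baseline means (change score): v = k² + 1 − 2kρ
- ideal baseline adjustment: v = 1 − ρ²
- difference: (k − ρ)², so optimal adjustment is never less precise before the cost of estimating the slope

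With k = 1 the ratio of adjusted to free variance is (1 + ρ)/2: 0.65, 0.75 and 0.85, a saving of 35%, 25% and 15%.

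**Power.** Change score: noncentral F(1,48) with noncentrality 0.66²/(0.0551·v). For k = 1 and ρ = 0.3 this is 0.4356/(0.0551·1.4) = 5.65, which gives 64.4%. Baseline covariate: F(1,47) with v = 1 − ρ². The variance is further multiplied by 1 + t²/48, where t is the chance baseline t statistic, and power is averaged over its distribution. This step charges for estimating the slope. Treating the slope as known would give 82.3/88.9/97.1% instead of 81.5/88.2/96.8%.

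| k | change score, ρ = 0.3/0.5/0.7 | baseline covariate |
|---|---|---|
| 1.0 | 64.4 / 78.7 / 94.5% | 81.5 / 88.2 / 96.8% |
| 0.8 | 72.5 / 85.2 / 96.9% | 81.5 / 88.2 / 96.8% |
| 0.6 | 78.7 / 88.5 / 96.9% | 81.5 / 88.2 / 96.8% |

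The gain is about 17/10/2 points at k = 1, 9/3/0 at k = 0.8 and 3/0/0 at k = 0.6. With 20 per arm (the 40 completers in the retention rule) and k = 1, the same formulas give 54/69/89% against 72/80/92%.

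**Effect of selecting on low RTQ.** As a crude stand-in for the eligibility rule, take normal scores (mean 2.57, SD 0.83) and enrol only those below 3.0. Baseline SD falls to 0.58 and k to 0.72/0.75/0.81, and the correlations fall to about 0.2/0.4/0.6. Change-score power is then 73/84/96%. The covariate analysis stays at about 81/88/97%, because selecting on baseline leaves the residual variance given baseline unchanged. The gain is about 9/4/1 points.

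**Worst case for adjustment.** When k = ρ the change score already weights baseline optimally. At ρ = 0.3 power goes from 82.3% to 81.5%, a loss of about 0.8 point.

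**Constraining baseline means under a random intercept only.** Baseline then receives weight equal to the fitted intraclass correlation instead of ρ/k. Take k = 0.6, ρ = 0.7, four visits and a common correlation. The average variance is (0.36 + 3)/4 = 0.84 and the average covariance is (3·0.42 + 3·0.7)/6 = 0.56, so the weight is 0.667. The variance factor is 1 + 0.667²·0.36 − 2·0.667·0.42 = 0.60, against 0.52 with free means. At k = 0.6 and ρ = 0.5 it is 0.80 against 0.76. The constraint can therefore lose precision under that structure.

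**The case against.** The strongest reply is that nothing in the plan is wrong. Hypothesis 4 concerns greater improvement, the interaction tests exactly that, and the model is standard and unbiased under randomisation. This stands: the point is about efficiency only. The reading with free baseline means is also an inference, since the text does not rule out a constraint.

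A reader might go further and infer that the 80% overstates the trial's power. The documents do not support that. Section 3.3 names the independent t-test and the post-intervention visit, and the figure reproduces for that test. With equal SDs the change-score contrast has less power than the t-test if ρ is below 0.5 and more if it is above. The documents give no ρ, so no direction of error can be claimed.

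It is also fair to say that the size of the gain is speculative. The largest gain needs a low correlation and no narrowing of the baseline SD, although eligibility selects on low scores.

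Two technical objections also stand and shape the fix. Adding the constraint without naming a covariance structure can do harm. Baseline adjustment also presumes that baseline is answered before assignment, which the documents do not state.

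**Conclusion.** The point holds as a cheap improvement with low stakes. On its ordinary reading the primary model is valid but generally less precise than a baseline-adjusted one. At 25 per arm, with follow-up SD 0.83 and a difference of 0.66, adjustment adds about 17 points of power for the post-intervention contrast at best in the range examined (ρ 0.3, equal SDs). It adds about 9/4/1 points under the crude selection scenario. It adds about nothing when baseline SD is near 0.6 of follow-up SD and ρ is 0.5 or more.

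These figures rest on assumed correlations, SD ratios, 1:1 allocation and complete data. The consequence is limited: sample size and the feasibility decision rules do not use RTQ, and efficacy is described as preliminary. The 80% needs no correction.

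**What to change.** Amend the Phase 3B Data Analysis paragraph in one of two ways.

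1. Analyse the follow-up RTQ scores with baseline RTQ as a covariate, allowing a separate baseline slope at each visit. Test the treatment and treatment-by-visit terms together, or a named visit contrast. In this form the interaction alone would test only whether the effect differs between follow-up visits.
2. Keep baseline as an outcome, constrain its mean to be equal across arms, and specify an unstructured covariance over the four visits. Do not impose the constraint under a random-intercept-only structure.

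In either case, state that the baseline survey is completed before assignment. Optionally, add to Section 3.3 that the 80% is not the power of the interaction test. As a separate tidy-up, reconcile the visit called 6-week there with the visit at about 8 weeks in Sections 3.1 and 4.2.

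The cost is wording only, with no new data. The statistical downside is at worst about 0.8 point of power at 25 per arm over the correlations examined, when the SD ratio equals the correlation. The covariate form also drops anyone with no follow-up visit. The constrained form keeps all observed data, as the plan intends.
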